ii-functional status scale (FSS)

Pain score (Visual analogue scale; VAS)

Quality of life score (SF 36 questionnaire)

9. Research methodology

This is a single center, randomized, double-blind, placebo-controlled trial conducted in University Putra Malaysia Teaching Hospital (HPUPM). Study period : 6 months Date of first subject enrolment :1st December 2023 Date of last subject completed: 30th September 2024 Target population : patients with symptoms of CTS Sampling frame : all patients referred to Neurology Department for clinical and electrodiagnostic examination of CTS. Sampling unit : patients with mild to moderate CTS Sampling method : universal sampling

All patients that presented to Neurology Clinic or Neurophysiology Laboratory with symptoms of hand numbness/tingling or pain in the median nerve distribution undergo a thorough physical examination based on current international guideline for diagnosis and assessment of CTS (15). This includes :

- Personal characteristics (eg, age, sex, weight, height, body mass index)
- Range of motion of hand/wrist
- Observation of deformity, swelling, atrophy, skin trophic changes
- Manual muscle testing of the upper extremity (eg, examine for muscular atrophy, especially in the thenar muscle group), pinch/grip strength
- Sensory examination
- Provocative tests (eg, Phalen test, Tinel sign, median nerve compression test, reverse Phalen test)

These patients then undergo an NCS, to determine the severity of CTS. The NCS will be carried out using the machine *Natus, USA, Synergy on Nicolet EDX NCS EMG EP System*. The NCS protocol follows the American Academy of Neurology/American Association of Neuromuscular and Electrodiagnostic Medicine/American Academy of Physical Medicine and Rehabilitation (AAN/AANEM/AAPMR) guidelines for diagnosis of CTS (15), which includes electrodiagnostic examination of :

- Sensory NCS studies to the median nerve with distal latency compared to the ulnar and radial nerve
- Median motor nerve conduction studies

If the clinical and NCS studies fulfil the diagnosis of CTS and fits the inclusion criteria for the study, they undergo randomisation into the treatment group or the control group. The treatment group will receive oral combination of alpha lipoic acid and vitamin B preparations, while the control group will receive a placebo. The treatment will be carried out for 6 months.

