Treatment group will receive oral combination of alpha lipoic acid and vitamin B. Composition: Alpha Lipoic Acid (300mg), Methylcobalamin (500mcg), Vitamin B1 (39mg) and Vitamin B6 (8mg), 2 tablets taken once daily (Bionerv).

Control group will receive placebo drug. Composition: Maltodextrin, Microcrystalline Cellulose, Tricalcium Phosphate, Silicon Dioxide, Magnesium stearate, 2 tablets taken once daily.

Inclusion and exclusion criteria

Inclusion criteria

- Age more than 18 years old
- Subjects with symptoms and physical examination of CTS
- Fulfil the electrodiagnostic criteria of mild to moderate CTS, defined based on the Padua Scale (16):
 - Minimal : abnormal segmental and comparative tests only
 - Mild : abnormal digit/wrist sensory nerve conduction velocity (SNCV) and normal distal motor latency (DML)
 - Moderate : abnormal digit/wrist sensory nerve conduction velocity (SNCV) and abnormal distal motor latency (DML)

Exclusion criteria

- Pregnant or breast feeding women
- Patients with history of trauma in the dominant hand
- Patients with symptoms of CTS but has normal NCS

- Patients with electrodiagnostic criteria of severe or extreme CTS as defined in the Padua scale (16):
 - severe : absence of sensory response (SNAP) and abnormal distal motor latency (DML)
 - extreme : absence of motor (CMAP) and sensory responses (SNAP)
- Patients who are taking traditional or complementary medication for CTS

Study procedure

The patients were randomized to receive oral combination of alpha lipoic acid and vitamin B; Bionerv (alpha lipoic acid; 300mg, methylcobalamin; 500mcg, vitamin B1; 39mg and vitamin B6; 8mg), 2 tablets once daily or placebo drug (maltodextrin, microcrystalline cellulose, tricalcium phosphate, silicon gioxide, magnesium stearate) 2 tablets once daily.

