SD – standard deviation = from previous studies or pilot study $Z\alpha/2 = Z \ 0.05/2 = Z \ 0.025 = 1.96$ (From Z table) at 80 % power at type 1 error of 5 % $Z \beta = Z \ 0.20 = 0/842$ (From Z table) at 80 % power d= effect size = difference between mean value

So, the formula: sample size: $2 \cdot SD^2(1.96 + 0.84)^2$ d^2 SD = 1.27 Za/2 = 1.96 Zb = 0.84 $d^2 = (0.81)^2 = 0.66$ $n = \frac{2(1.27)^2 (1.96 + 0.84)^2}{(0.81)^2}$

= 2 (1.61) (7.84)

0.66

= 38 in each arm (Total 76 patients)

Operational definitions

Primary outcome measure

The primary outcome was the electrodiagnostic improvement of the median nerve on NCS before the before the intervention (visit 1) and at three-months (visit 2) and six- months (visit 3). The NCS parameters that are analysed were:

- 1. Distal sensory latency; DSL (normal value for DSL <3.5ms)
- 2. Sensory nerve action potential; SNAP (normal value for SNAP >2.5 μ V)
- 3. Conduction velocity; CV (normal value for CV >50m/s)
- 4. Distal Motor Latency; DML (normal value for DSL <4ms)
- 5. Compound muscle action potential; CMAP (normal value for CMAP>4.0 mV).

Secondary outcomes measures

- Tolerability and safety of oral combination of alpha lipoic acid and vitamin B preparations
- The improvement of scores in Boston Carpal Tunnel Questionnaires (BCTQ) by the SSS scale prior to the intervention, at 3 months and at 6 months
- The improvement of scores in Boston Carpal Tunnel Questionnaires (BCTQ) by the FSS scale prior to the intervention, at 3 months and at 6 months
- The improvement of pain scores in VAS prior to the intervention, at 3 months and at 6 months
- The improvement of quality of life score SF 36 prior to the intervention, at 3 months and at 6 months

Data collection

[figure not shown]
Protection of human rights is the utmost priority for researchers. We obtain informed consent from all participants in this research. The consent process included giving full and comprehensible information about the research and clear assurance of their voluntary

participation. Beneficence is the essence of concern for the well-being of the participants whereby the risk of harm was the least possible.

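### The mild-to-moderate inclusion criterion also admits the Padua grade Minimal, which contradicts the stated population and may dilute the primary comparison

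*Combined protocol and SAP*

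**What the plan says.** Section 6 (Research objectives and hypotheses) sets the general objective, and each specific objective, in mild to moderate disease. Section 9 (Research methodology) repeats this: "Sampling unit : patients with mild to moderate CTS".

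The Inclusion criteria carry the same label, "Fulfil the electrodiagnostic criteria of mild to moderate CTS, defined based on the Padua Scale (16"), but three grades follow:

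- The first is "Minimal : abnormal segmental and comparative tests only".
- The second is Mild, where the sensory velocity from digit to wrist is abnormal but the motor latency is not.
- The third is Moderate, where both of these are abnormal.

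Two of the Exclusion criteria concern electrodiagnostic grade. One removes "Patients with symptoms of CTS but has normal NCS". The other removes "Patients with electrodiagnostic criteria of severe or extreme CTS as defined in the Padua scale (16").

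Section 8 and Operational definitions (Primary outcome measure) name five median nerve parameters: distal sensory latency (DSL), sensory action potential (SNAP), conduction velocity (CV), distal motor latency (DML) and compound motor action potential (CMAP). Each has a normal limit, for example "Conduction velocity; CV (normal value for CV >50m/s"). The segment for CV is not stated.

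Section 8 lists severity as an independent variable. Randomisation describes no stratification by severity, and section 10 specifies no severity covariate or subgroup. Section 10 puts every randomised subject in the analysis (Analyses sets) and all eligible patients in the primary comparison (Efficacy Analysis).

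**The concern.** Two things do not fit together. First, the eligibility list is wider than the population named in the objective, so whether a Minimal patient belongs in the trial depends on which section the site follows. That settles who is enrolled and which population the conclusion describes.

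Second, the primary outcome is improvement in parameters on which a Minimal patient is expected to start at or near normal. If such patients contribute little treatment difference, the average effect over all randomised patients is pulled toward zero. Nothing in the analysis plan would separate them out.

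**Working it through.** **Step 1: are Minimal patients eligible as written?** The grade is on the inclusion list. The low-end exclusion needs a normal study, and a Minimal patient has abnormal segmental or comparative tests. The high-end exclusion covers severe and extreme only. So they are eligible.

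**Step 2: what is normal at entry?** Abnormal digit/wrist sensory velocity is what turns a case into Mild, and abnormal DML is what turns it into Moderate. The word *only* in the Minimal definition therefore implies that both are normal. Normal DSL, SNAP and CMAP are a reasonable inference from the same word, but the definitions do not say so.

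**Step 3: does the primary outcome include what is abnormal?** None of the five parameters is named as a segmental or comparative test. Section 9 does describe a comparative study, of median distal latency against the ulnar and radial nerves, but that comparison is not a primary parameter.

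**Step 4: the plan's sample size.** Sample size estimation uses n = 2·SD²·(1.96 + 0.84)²/d² with SD = 1.27 and d = 0.81:

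- 2 × 1.61 × 7.84 / 0.66 = 38.25 with the plan's rounded terms, and 38.55 unrounded. The stated 38 per arm is reproduced, apart from rounding up to 39.
- The standardised effect is 0.81/1.27 = 0.638.

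This base is not sound. The source figures quoted are 1.07 ± 1.27 and 0.83 ± 0.81, so 0.81 is the second group's SD, and the means differ by 1.07 − 0.83 = 0.24. The outcome is limitation of everyday activity, not nerve conduction. What follows shows the mechanism and is not the trial's power.

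**Step 5: dilution under stated assumptions.** Let m be the share of Minimal patients and r their effect relative to the others. Neither is in the documents. The SD is held at 1.27.

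- Diluted effect: e = 0.638 × [1 − m(1 − r)]
- Power: two-sided 5% two-sample t test, noncentrality e·√(n/2), 2n − 2 degrees of freedom
- Without Minimal patients, n = 38: noncentrality 0.638 × √19 = 2.78, power 78.3%

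| Share Minimal (m) | No effect (r = 0): e, power | Half effect (r = 0.5): e, power | Left out, not replaced: n per arm, power |
|---|---|---|---|
| 10% | 0.574, 69.5% | 0.606, 74.1% | 34, 73.6% |
| 20% | 0.510, 59.3% | 0.574, 69.5% | 30, 68.1% |
| 30% | 0.446, 48.4% | 0.542, 64.5% | 27, 63.3% |

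If Minimal patients respond like the others (r = 1), keeping them costs no power.

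**Step 6: break-even.** Leaving them out and keeping them give the same noncentrality when 1 − m(1 − r) = √(1 − m), that is r = 1 − [1 − √(1 − m)]/m. For m = 10%, 20% and 30% this is 0.49, 0.47 and 0.46. With the whole-number group sizes in the table it is 0.44, 0.43 and 0.46. Exclusion without replacement therefore gains power only if the effect in Minimal patients is below about half that in the rest.

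**The case against.** The strongest reply is that the contradiction is one of labels: the criterion spells out which grades it means, and admitting early disease is a legitimate choice for a treatment with a neuroprotective rationale. The choice is open to the sponsor. It does not remove the contradiction, because the same list names Mild and Moderate as separate grades and every other statement of the population stops at those two.

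A reader might infer that Minimal patients cannot improve on the primary outcome. The documents do not support that. The plan sets normal limits but no responder or normalisation rule, the parameters are continuous, and they can change within the normal range. Deterioration on placebo over six months could also produce a difference.

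A reader might also infer that these patients are measured on nothing that was abnormal. That is not shown either. Median sensory latency is one component of the comparative test described in section 9, DSL is a primary parameter, and the CV segment is unstated.

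A limited floor is not peculiar to Minimal, since Mild patients have normal DML by definition. They do, however, have abnormal sensory velocity, and Minimal patients have neither abnormality.

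The objection to the power figures stands in full. The share and the response of Minimal patients are assumed, and the base effect is invalid for this outcome. With the quoted difference of 0.24 and SD 1.27, power at 38 per arm is about 13% before any dilution, and about 11% to 9% with 10% to 30% of patients showing no effect. No reader should conclude that this trial's power drops from 78.3% to 48.4%, or that excluding Minimal patients always raises power.

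**Conclusion.** The inconsistency is established from the text: Minimal patients are eligible in a trial whose objectives and sampling unit say mild to moderate. It is also established that they enter with normal digit/wrist sensory velocity and normal DML, and that no segmental or comparative test is a primary parameter.

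Dilution is plausible but of unknown size. It rests on two quantities that the plan does not give: the share of Minimal patients, and their effect relative to the others. The illustrated loss at 38 per arm runs from none (equal effect) to about 30 percentage points (78.3% − 48.4%, with 30% Minimal and no effect), on a base effect that is itself unsound. The case for action is the mismatch between the population enrolled and the population named. It does not depend on the power figures.

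**What to change.** Make the population analysed match the stated objective, in one of three ways:

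1. Remove the Minimal line from the Inclusion criteria and list that grade with the excluded ones.
2. Keep these patients, define the primary analysis as those graded Mild or Moderate at Visit 1, and report Minimal separately. The grade is set before randomisation, so the restricted comparison stays unbiased. The statement under Analyses sets that all randomised subjects are analysed must be amended, and Efficacy Analysis brought into line with it.
3. If Minimal is wanted in the primary population, write minimal to moderate in the objectives, the sampling unit, the criterion heading and the conclusion, and prespecify baseline severity as a covariate.

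Under any option, state the segment to which CV refers.

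The cost is a line of eligibility text or a few sentences in the analysis section. The downside is slightly slower recruitment under the first option and a smaller primary set under the second. The third keeps the numbers but accepts whatever dilution occurs.

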During visit 1, a thorough history and physical examination were done, and demographic data was collected. Afterward, the patients were required to answer three sets of selfadministered questionnaires: Boston Carpal Tunnel Questionnaire (BCTQ), Visual analogue score (VAS) and SF-36. The BCTQ is a specific questionnaire for assessing CTS that consists of two distinct scales, the Symptom Specific Scale (SSS) which has 11 items and the Functional Status Scale (FSS) containing 8 items. Each scale generates a final score ranging from 1 to 5, with a higher score indicating greater disability and poor symptoms control. BCTQ is a reliable questionnaire to assess CTS owing to its high cross-cultural adaptation and multilingual validity and reliability (17-18). The VAS is a visual scale with 0 scored as "no pain" and 10 as "worst pain imaginable" and serves as an excellent tool for pain score with excellent validity and reproducibility (19-20). The SF-36 is a quality-of-life questionnaire that comprises of 36 questions covering eight domains of health which are; Physical Functioning (PF), Role Limitations due to Physical Health, Role Limitations (RL) due to Emotional Problems (RE), energy/fatigue, emotional well-being, social functioning, pain, and general health (GH) where a higher score indicates a better outcome (21). After the administration of these questionnaires, they will be subjected for a nerve conduction study (NCS) to determine the severity of CTS. The NCS were performed by the same trained personnel to ensure consistency and accuracy. A Patient-Reported Questionnaire to monitor any side effects were used to assess the tolerability of the drugs.

The patients were reassessed at Visit 2 (3 months post-treatment) and Visit 3 (6 months post-treatment). During each visit, they underwent physical examination, NCS, and were required to complete the three sets of questionnaires (BCTQ, VAS, and SF-36). They were also required to fill in the form regarding the side effects of the treatments. The investigators made a phone call and sent reminder message at the 6th and 18th week to ensure compliance, medication adequacy and follow up review. During the study, patients were allowed to undergo the standard of care treatment at our center such as physiotherapy.

Fig. 1 The visual analogue scale (VAS).

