The final code is only known to the statistician and the document will be stored in a secure locked safe. The following information will be recorded during the randomization; study ID (assigned during the study initiation), investigator password (assigned during the initiation), subjects screening status, date of informed consent signed by subject, subject's ID no (e.g., Last 4 digits of IC), upon successful randomization, the subjects will be assigned randomization number and treatment. The subject's ID no. and randomization no. will be documented on the Patient Enrolment Log and Patient Identification List.

Blinding and emergency unblinding procedures

The participants and outcome assessor of the study is blinded about the allocation status of the participants. In the setting of an adverse event (AE), for which knowledge of the identity of the test drug is necessary to manage the subject's condition, the sealed emergency code key for that subject may be broken and the test drug identified by the medical monitor. The medical monitor will have a set of sealed emergency code keys (one for each subject) kept in a secured location and he/she will be accessible at all times by telephone. The medical monitor is medical officer who is working in the hospital. He/she is familiar with hospital system and is also aware of the study protocol. Should emergency code key for that subject, identify the test coil and inform the investigator. A detailed report with the date and reason for identifying the study drug will

be prepared by the medical monitor and attached to the case report form. This report must be signed by the medical monitor and the investigator. All unused sealed code keys will be accounted for at the end of the study.

Except in the case of emergency, the treatment blind will be maintained until all subjects have completed the treatment and the database has been cleaned and locked. Any broken code will be clearly justified and explained by a comment on the case report form, along with the date on which the code was broken.

Sample size estimation

Sample size calculation was performed using the study published by Pajardi et al. Sample size was calculated based on improvement to limitations of everyday activity among the patients with CTS as the outcome parameter (1.07 ± 1.27 vs 0.83 ± 0.81). The marginal error (α) was set at 0.05.

Sample size: $2 \frac{\text{SD}^2(2\alpha/2 + Z\beta)^2}{d^2}$

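### The only routine safety instrument the protocol names is a patient-completed side-effects form, so medical events that patients do not regard as side effects may be missed

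*Combined protocol and SAP*

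**What the plan says.** **What is promised.** Research question b in section 5 asks whether the combination is safe. The conceptual framework in section 8 lists tolerability alone as a secondary outcome. Operational definitions in section 9 widens this to "Tolerability and safety of oral combination of alpha lipoic acid and vitamin B preparations". Section 10 has a Safety Analysis paragraph. It defines the safety population as randomised patients with at least one dose, grouped by treatment actually received, but does not say which events are counted.

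**What is collected.** Section 9, Study procedure, names the instrument while describing visit 1: "A Patient-Reported Questionnaire to monitor any side effects were used to assess the tolerability of the drugs". For the visits at 3 and 6 months it adds: "They were also required to fill in the form regarding the side effects of the treatments". Those visits also include a physical examination, NCS, BCTQ, VAS and SF-36, none of which is described as a way of collecting adverse events. Between visits the investigators telephone and "sent reminder message at the 6th and 18th week to ensure compliance, medication adequacy and follow up review". Adverse events are not among the stated purposes.

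**Where adverse events are mentioned.** The term appears under Blinding and emergency unblinding procedures, as the trigger for a code break: "In the setting of an adverse event (AE), for which knowledge of the identity of the test drug is necessary". The medical monitor then writes a report that is attached to the case report form. The text does not link that report to the safety summaries in section 10.

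**The concern.** A side effect is an event already judged to be caused by treatment. A form that asks about the side effects of the treatments therefore invites the patient to decide on cause before writing anything down. A fall, a hospital admission or a rash that the patient blames on something else may not be entered.

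In a randomised, placebo-controlled trial the patient does not need to make that judgement. If all events are recorded whatever their cause, the comparison of the two arms shows whether the product produces an excess. Events that depend on patient suspicion are least likely to be recorded when the effect is unexpected, which is where a control arm helps most. At stake is whether a low count at the end of this trial can support an answer to research question b, or only a statement about effects that patients themselves linked to the tablets.

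**Working it through.** **Inputs.** The arm size is 38, from Sample size estimation in section 9. The plan's own calculation reproduces: 2 × 1.61 × 7.84 / 0.66 = 38.2, or 38.5 without rounding the inputs. Whether those inputs are the right ones is a separate matter; 38 serves here only as a denominator. The documents give neither an expected event rate nor the share of events the form would capture. I assume capture shares c of 100%, 75%, 50% and 25%, applied independently to each patient with the event, and I assume all 38 are dosed and followed.

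**1. What zero recorded events would exclude.** If the true rate is p, the recorded rate is c × p. The one-sided 95% upper limit after 0 events in 38 solves (1 − c × p)^38 = 0.05, so

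p = [1 − 0.05^(1/38)] / c = 0.0758 / c.

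| Assumed capture c | Zero events excludes a true rate above |
|---|---|
| 100% | 7.6% |
| 75% | 10.1% |
| 50% | 15.2% |
| 25% | 30.3% |

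**2. The chance of seeing an event at all.** For an assumed true rate of 5% in one arm, the chance of at least one recorded event is 1 − (1 − 0.05c)^38.

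| Assumed capture c | Chance of at least one recorded event |
|---|---|
| 100% | 86% |
| 75% | 77% |
| 50% | 62% |
| 25% | 38% |

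**3. What happens to the comparison of arms.** If capture is the same in both arms, the recorded difference is c × pA − c × pB = c × (pA − pB). It shrinks in proportion to c but keeps its sign, and it is zero when there is no true difference. The loss is in counts and sensitivity, not in direction.

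**4. The text read as a whole.** I compared every mention of safety, tolerability, side effects and adverse events. The readable text has no definition of an adverse event independent of cause, no described enquiry by an investigator about all events, and no recording of seriousness or relatedness.

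**The case against.** The strongest reply is that the form itself is not in the documents. It is named only in passing, once as monitoring any side effects, and a neutral symptom checklist could carry that name without asking the patient to judge cause. The data-collection figure and the flowchart are also missing. This stands. A reader might infer that unattributed events definitely go unrecorded and that the safety outcome merely measures what patients believe. The documents do not show that; they support only a risk. Even a closed checklist, however, would miss unlisted events unless it had an open question.

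A reader might also infer that the form is the sole source of safety information. The unblinding procedure is a second route onto the case report form, and the visits include an examination. That route is narrow, and neither is tied to the safety summaries, so the accurate statement is that the form is the only routine instrument named.

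Two further inferences fail:

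- **A worsening hand would be lost.** It would be picked up by the repeated examination, NCS, BCTQ and VAS, whatever the patient thinks caused it.
- **Events needing a code break might not reach the medical monitor.** The stated trigger is a clinical need to know the drug's identity and does not depend on the form.

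Finally, participants are blinded. If blinding holds, filtering by belief should act alike in both arms absent a drug effect, so the comparison of recorded events is not invalidated. This also stands. The single-arm limits above illustrate lost information and do not measure bias between arms. Even the 7.6% with full capture is a limit set by the sample size.

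**Conclusion.** The concern holds as a gap in specification with a plausible cost. Safety is a named outcome, the only routine instrument named is framed by cause, and no cause-neutral collection is described. Events that patients do not see as side effects may be missed. That would lower counts in both arms and weaken the trial's ability to show an unsuspected excess, without necessarily favouring either arm.

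The size cannot be derived from the documents. On the assumed capture range of 75% to 25%, the rate excluded by zero events in an arm of 38 rises from 7.6% to between about 10% and 30%. If the unseen form is already neutral as to cause and has an open question, the collection gap largely closes, and what remains is to say so and to state which events section 10 counts.

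This is worth correcting because the change is cheap. It is not a demonstrated failure of measurement, and it does not touch the primary outcome.

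**What to change.** - **Form and section 9, Study procedure.** Record every new or worsened medical event since the last contact, whatever its believed cause. Do this at Visits 2 and 3 and at the week 6 and week 18 calls already planned.
- **Assessment.** Have existing staff who are blinded to allocation, for example the blinded outcome assessor, record seriousness and an opinion on relatedness. Keep these as separate items from the event itself.
- **Section 10, Safety Analysis.** Tabulate all events by arm as the main safety summary, with events considered related as a secondary table. State whether events documented in code-break reports are included.

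The cost is rewording one form and two protocol sections, plus a few more minutes per contact. Reported counts will rise in both arms and will include events unrelated to treatment. No extra visit, procedure or staff is needed.
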